6.4 Supportive Care

Subjects should receive full supportive care, including transfusions of blood and blood products, antibiotics, anti-emetics, etc., when appropriate. Subjects who require therapeutic anticoagulation with low molecular weight heparin (e.g., enoxaparin and tinzaparin), coumadin or other oral anticoagulants at study entry will be eligible for enrollment. In addition, subjects requiring therapeutic anticoagulation with these agents during study participation will be allowed to remain on study therapy.

6.4.1 Treatment of Nivolumab or Ipilimumab-Related Infusions Reactions

Since nivolumab and ipilimumab contain only human immunoglobulin protein sequences, each is unlikely to be immunogenic and induce infusion or hypersensitivity reactions. However, if such a reaction were to occur, it might manifest with fever, chills, rigors, headache, rash, pruritis, arthralgias, hypo- or hypertension, bronchospasm, or other symptoms. All Grade 3 or 4 infusion reactions should be reported within 24 hours to the BMS Medical Monitor and reported as an SAE if criteria are met. Infusion reactions should be graded according to NCI CTCAE (v4) guidelines. Treatment recommendations are provided below and may be modified based on local treatment standards and guidelines as appropriate:

Grade 1 Symptoms: Mild reaction; infusion interruption not indicated; intervention not indicated.

- Remain at bedside and monitor subject until recovery from symptoms. The following prophylactic premedications are recommended for future infusions: diphenhydramine 50 mg (or equivalent) and/or acetaminophen 325 to 1000 mg at least 30 minutes before additional nivolumab or ipilimumab administrations.

Grade 2 Symptoms: Moderate reaction requires therapy or infusion interruption but responds promptly to symptomatic treatment [eg, antihistamines, non-steroidal anti-inflammatory drugs, narcotics, corticosteroids, bronchodilators, IV fluids]; prophylactic medications indicated for ≤ 24 hours.

- Stop the nivolumab or ipilimumab infusion, begin an IV infusion of normal saline, and treat the subject with diphenhydramine 50 mg IV (or equivalent) and/or acetaminophen 325 to 1000 mg. Remain at bedside and monitor subject until resolution of symptoms. Corticosteroid or bronchodilator therapy may also be administered as appropriate. If the infusion is interrupted, then restart the infusion at 50% of the original infusion rate when symptoms resolve; if no further complications ensue after 30 minutes, the rate may be increased to 100% of the original infusion rate. Monitor subject closely. If symptoms recur then no further nivolumab or ipilimumab will be administered at that visit. Administer diphenhydramine 50 mg IV, and remain at bedside and monitor the subject until resolution of symptoms. The amount of study drug infused must be recorded on the electronic case report form (eCRF). The following prophylactic premedications are recommended for future infusions: diphenhydramine 50 mg (or equivalent) and/or acetaminophen 325 to 1000 mg should be administered at least 30 minutes before additional nivolumab or ipilimumab administrations. If necessary, corticosteroids (recommended dose: up to 25 mg of IV hydrocortisone or equivalent) may be used.

Grade 3 or Grade 4 symptoms: Severe reaction, Grade 3: prolonged [ie, not rapidly responsive to symptomatic medication and/or brief interruption of infusion]; recurrence of symptoms following initial improvement; hospitalization indicated for other clinical sequelae [eg, renal impairment, pulmonary infiltrates]). Grade 4: (life-threatening; pressor or ventilatory support indicated).

- Immediately discontinue infusion of nivolumab or ipilimumab. Begin an IV infusion of normal saline, and treat the subject as follows. Recommend bronchodilators, epinephrine

0.2 to 1 mg of a 1:1,000 solution for subcutaneous administration or 0.1 to 0.25 mg of a 1:10,000 solution injected slowly for IV administration, and/or diphenhydramine 50 mg IV with methylprednisolone 100 mg IV (or equivalent), as needed. Subject should be monitored until the investigator is comfortable that the symptoms will not recur. Nivolumab or ipilimumab will be permanently discontinued. Investigators should follow their institutional guidelines for the treatment of anaphylaxis. Remain at bedside and monitor subject until recovery from symptoms. In the case of late-occurring hypersensitivity symptoms (eg, appearance of a localized or generalized pruritis within 1 week after treatment), symptomatic treatment may be given (eg, oral antihistamine, or corticosteroids).

6.5 Criteria for Taking a Participant Off Protocol Therapy

Duration of therapy will depend on individual response, evidence of disease progression and tolerance. In the absence of treatment delays due to adverse event(s), treatment may continue until one of the following criteria applies:

- Disease progression (unless otherwise specified in section 6.7)
- Intercurrent illness that prevents further administration of treatment
- Unacceptable adverse event(s)
- Subject demonstrates an inability or unwillingness to comply with the oral medication regimen and/or documentation requirements
- Subject decides to withdraw from the protocol therapy
- General or specific changes in the subject's condition render the subject unacceptable for further treatment in the judgment of the site investigator
- Female subject becomes pregnant
- Protocol therapy is interrupted for > 6 weeks (unless otherwise specified in 6.3).

Participants will be removed from the protocol therapy when any of these criteria apply. The reason for removal from protocol therapy, and the date the participant was removed, must be documented in the case report form (CRF). Alternative care options will be discussed with the participant.

An ODQ Treatment Ended/Off Study Form will be filled out when a participant is removed from protocol therapy. This form can be found on the DF/HCC website at [http://www.dfhcc.harvard.edu/research/clinical-research-support/document-library-forms-sops- etc/](http://www.dfhcc.harvard.edu/research/clinical-research-support/document-library-forms-sops-etc/).

In the event of unusual or life-threatening complications, treating investigators must immediately notify the Overall PI, [REDACTED]

6.6 Duration of Follow Up

Subjects will have safety follow up visits at D30 following the last dose of study drug. Subjects who have an ongoing study treatment-related AE upon study completion or at discontinuation from the study will be followed until the event has resolved to baseline grade, the event is assessed by the site investigator as stable, new anticancer treatment is initiated,

the subject is lost to follow-up, the subject withdraws consent, or until it has been determined that study treatment or participation is not the cause of the AE. If not seen in clinic, subjects will be called on day 100 (+/-3) following the last dose of study drug for assessment of adverse events.

After progression/treatment discontinuation, subjects will be followed for survival and receipt of next line therapies every 6 months until death or 2 years after end of treatment visit. Follow-up will be via phone calls and through review of medical records.

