- 9: Long term follow-up for survival and initiation of a new anti-cancer treatment will occur every 6 months (\pm 14 days) until death or 2 years after EOT visit whichever comes first. This follow up may be via phone calls and through review of medical records.
- 10: An OPTIONAL tumor biopsy at time of progression will be requested from subjects unless the procedure is deemed medically unsafe or not feasible.

ARM A subjects will have biopsies (1) following progression off nivolumab prior to reinitiation of nivolumab (ideally prior to restart but within 10 days of re-starting nivolumab is permitted if scheduling issues and clinical need to start sooner than biopsy can be obtained), (2) at progression following treatment with both nivolumab and ipilimumab. For patients enrolled on ARM A in the Single Cell Sequencing Cohort a mandatory biopsy will be performed at baseline, an optional biopsy at the time of response following discontinuation of nivolumab and a mandatory biopsy at time of permanent treatment discontinuation/off study if deemed safe and feasible. Biopsies should be performed per institutional standards and/or operator preference. Blood samples should be drawn within 2 weeks of the biopsy to document an acceptable coagulation profile (INR \leq 1.5, PTT \leq 60, platelets $>$ 50,000). Aspirin and NSAIDS should be discontinued 5 days prior to the biopsy. Please see the laboratory manual for additional collection, labeling and shipping information.

11: MANDATORY: Blood samples for Biomarkers will be collected every 2 cycles (\pm 7 days) prior to treatment, corresponding to all imaging assessment time points and at time of EOT visit. Additionally, blood samples for biomarkers will be collected at confirmatory imaging assessment time points. If EOT collection is within 2 weeks of prior collection, research samples do not need to be collected. For patients enrolled on the Single Cell Sequencing Cohort, whole blood for CTC collection and whole blood for plasma/PBMC isolation will not be collected.

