7: End of treatment (EOT) visit will occur 30 days (\pm 7 days) after last dose of study drug. Subjects will come off study treatment if they have PD as described in bullet #6 or for other reasons such as toxicity or subject choice. Subjects who (1) had study drugs delayed or modified due to toxicity or other factors and (2) were then discontinued from study treatment can use a study visit as EOT visit. Subjects who have an ongoing study treatment-related AE upon discontinuation from the study treatment will be followed until the event has resolved to baseline grade, the event is assessed by the site investigator as stable, new anticancer treatment is initiated, the subject is lost to follow-up, the subject withdraws consent, or until it has been determined that study treatment or participation is not the cause of the AE. If not seen in clinic, subjects will be called on day 100 (\pm 3) following the last dose of study drug for assessment of adverse events.

8: Long term follow-up for survival and initiation of a new anti-cancer treatment will occur every 6 months (\pm 14 days) until death or 2 years after EOT visit whichever comes first. This follow up may be via phone calls and through review of medical records.

9: An OPTIONAL tumor biopsy at time of progression will be requested from subjects unless the procedure is deemed medically unsafe or not feasible. For patients enrolled on the Single Cell Sequencing Cohort a mandatory biopsy will be performed at the time of treatment discontinuation/off study following treatment with nivolumab and ipilimumab if deemed safe and feasible. Arm B (1) following progression on treatment with BOTH nivolumab and ipilimumab. Biopsies should be performed per institutional standards and/or operator preference. Blood samples should be drawn within 2 weeks of the biopsy to document an acceptable coagulation profile (INR \leq 1.5, PTT \leq 60, platelets $>$ 50,000). Aspirin and NSAIDS should be discontinued 5 days prior to the biopsy. Please see the laboratory manual for additional collection, labeling and shipping information.

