8.1 Duration of Follow Up

Subjects who have an ongoing study treatment-related AE upon end of treatment visit will be followed until the event has resolved to baseline grade, the event is assessed by the site investigator as stable, new anticancer treatment is initiated, the subject is lost to follow-up, the subject withdraws consent, or until it has been determined that study treatment or participation is not the cause of the AE. After progression/treatment discontinuation, subjects will be followed for survival and receipt of next line therapies every 6 months until death or 2 years after treatment discontinuation. Follow-up will be via phone calls and through review of medical records.

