13.2.2 Definition of Secondary Endpoints

- Progression-free survival (PFS): defined as the time from nivolumab discontinuation (Arm A) or from ipilimumab initiation (Arm B) until documented progression by

RESIST criteria or death from any cause, censored at date last known progression-free for those who are alive and have not progressed.

- Overall Survival (OS): defined as the time from nivolumab discontinuation (Arm A) or from ipilimumab initiation (Arm B) until death from any cause, censored at date last known alive or at the time of last assessment of follow-up.
- Salvage therapy-free interval: defined as time from nivolumab discontinuation (arm A) to the receipt of re-starting nivolumab.
- Immune related objective response rate defined according to immune-related Responses Criteria (irRC) and detailed in section 10.5.
- Safety and tolerability according to NCI CTCAE v4.

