A total accrual goal is 83 subjects. Subjects will continue study therapies till disease progressions, withdraw or adverse events. Additional 2-year follow-up after the end of treatments (EOT) is planned. The primary study analysis is expected to be at 2 years; 6 months for accrual, and 18 months from enrollment for last subject.

Accrual Targets				
Ethnic Category	Sex/Gender			
	Females		Males	Total
Hispanic or Latino	2	+	2	= 4
Not Hispanic or Latino	24	+	55	= 79
Ethnic Category: Total of all subjects	26	+	57	= 83
Racial Category				
American Indian or Alaskan Native	2	+	3	= 5
Asian	2	+	5	= 7
Black or African American	2	+	6	= 8

Native Hawaiian or other Pacific Islander	0	+	0	=	0
White	20	+	39	=	59
Racial Category: Total of all subjects	26	+	53	=	83

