13.7.2 Secondary Analysis

PFS and OS: The progression-free survival (PFS), and overall survival (OS) will each be summarized using the product-limit method of Kaplan-Meier. Median times for each endpoint will be presented with two-sided 90% confidence intervals estimated using log(-log(survival)) methodology. Kaplan-Meier estimates of PFS at 6 or 12 months may also be presented with two-sided 90% confidence intervals.

Salvage Therapy-Free Interval: The proportion of subjects re-start nivolumab since nivolumab discontinuation (arm A) during 1-year will be estimated with two-sided 90% confidence intervals. In addition, the reasons for re-starting nivolumab (Arm A) will be tabulated.

Subset analysis of study endpoints will be explored according to IMDC* risk group (favorable, intermediate, versus poor risk); prior systemic treatment for RCC (yes versus no); first line versus second line targeted therapy; histology (clear cell versus non-clear cell RCC subtypes; sarcomatoid components present versus absent)

*IMDC risk factors include ECOG < 1, time from original diagnosis to treatment less than one year, hemoglobin less than the lower limit of normal, and serum calcium, neutrophil count, or platelet count greater than the upper limit of normal

Immune Related Objective Response Rate: The proportion of subjects with immune ORR will be presented with two-sided 90% confidence interval estimated using exact binomial methods.

Safety and Tolerability: All adverse events recorded during the trial will be summarized for the safety population. The incidence of events that are new or worsening from the time of first dose of treatment will be summarized according to system organ class and/or preferred term, severity (based on CTCAE version 4), type of adverse event, and relation to study treatment.

The worst grade will be used if any toxicity event is reported multiple times on the same participant. All adverse events resulting in discontinuation, and/or dosing interruption, and/or treatment delay will also be summarized.

Given the potential multiple treatment sequences, the incidence of events (grade 3+) will be summarized according to treatment arms as well as the type of therapies they are on at the time of events.

Deaths reportable as SAEs and non-fatal serious adverse events will be listed by patient and tabulated by primary system organ class, and type of adverse event.

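### Survival follow-up stops two years after each subject's own end of treatment, so Kaplan-Meier OS beyond about 24 to 25 months is subject to outcome-dependent censoring

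*Combined protocol and SAP*

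**What the plan says.** Section 6.6 follows subjects for survival after progression or treatment discontinuation, by phone and record review, "every 6 months until death or 2 years after end of treatment visit". The Arm A and Arm B calendar footnotes in Section 8 agree ("until death or 2 years after EOT visit whichever comes first"), and so does Section 13.3: "Additional 2-year follow-up after the end of treatments (EOT) is planned". Section 8.1 counts from a different date: "every 6 months until death or 2 years after treatment discontinuation". The calendar footnotes time the visit itself: "End of treatment (EOT) visit will occur 30 days" (± 7 days) after the last dose of study drug.

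Treatment length is itself an outcome. Section 13.3 states: "Subjects will continue study therapies till disease progressions, withdraw or adverse events". Under Section 2.7, Arm B stops treatment at PD. Arm A stops nivolumab and is observed until PD, then restarts nivolumab, and adds ipilimumab after a further PD.

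Section 13.2.2 starts OS at nivolumab discontinuation (Arm A) or ipilimumab initiation (Arm B), "censored at date last known alive or at the time of last assessment of follow-up". In Section 13.7.2, "overall survival (OS) will each be summarized using the product-limit method of Kaplan-Meier", with medians and 90% confidence intervals. No common survival cut-off, limit on the curve or sensitivity analysis for dependent censoring is given.

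**The concern.** Kaplan-Meier treats a censored subject as having the same future risk as those still followed. Here, among subjects still alive, those who stopped treatment earliest leave the risk set first. If they die faster than those still on treatment or in observation, the remaining risk set is healthier than the arm it stands for, and the late curve is too high. At stake are the OS curve beyond two years, any median reached there, and upper confidence limits that extend there. The protocol's own reference median OS on nivolumab is 25.0 months (Section 2.2), close to where the cap begins to act.

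**Working it through.** **When the cap acts.** The EOT visit is about 1 month after the last dose, so censoring time is about C = T + 1 + 24 = T + 25 months, with T the time from OS origin to last dose. (Section 8.1 would give T + 24.) In Arm B, a last dose at month 4 gives C = 29, and a last dose at month 24 gives C = 49. As T cannot be negative in Arm B, nobody is capped before about 24 to 25 months.

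**The primary analysis.** Section 13.3 schedules it at 6 + 18 = 24 months. OS starts only after initial nivolumab. With the first scan at about 2 months, the longest OS time is about 22 months, and the cap affects 0% of subjects. If accrual takes longer than 6 months, some subjects could reach the cap before the analysis, but estimates to 24 months would still be unaffected.

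**Arm B after 24 months.** The documents give no survival after EOT, so every rate here is an assumption. Time on treatment T is exponential, with median 4 to 8 months in non-responders and 30 in responders (10% to 30% of subjects). Post-EOT survival P is exponential with median 12 to 24 months. The on-treatment death hazard is 0.003 per month (time D0). Death is at D0 if D0 < T, otherwise at T + P. Censoring is at EOT + 25. True OS is compared with Kaplan-Meier OS in a large simulation.

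One case (medians 4 and 18 months, 20% responders):

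| Months from ipilimumab start | 24 | 30 | 36 | 48 | 60 |
|---|---|---|---|---|---|
| True OS, % | 55.4 | 46.0 | 38.1 | 26.3 | 18.3 |
| Kaplan-Meier OS, % | 55.4 | 46.5 | 40.1 | 32.0 | 26.6 |
| Mean at risk of 57, with cap | 31.6 | 16.8 | 9.9 | 5.2 | 3.6 |
| Mean at risk of 57, no cap | 31.6 | 26.2 | 21.8 | 15.0 | 10.4 |

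Kaplan-Meier minus true OS across the assumed range:

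- Constant post-EOT hazard: 0.0 points to 24 months, +0.9 to +2.2 at 36, and +3.0 to +5.9 at 48.
- Post-EOT risk varying between subjects (gamma frailty, variance 0.5 to 1.0, 20% responders): 0.0 to +0.9 at 36 and 0.0 to +2.9 at 48.
- Equal hazard on and off treatment (control): at most 0.1.
- One common cut-off at 60 months from study start (control): 0.0 at 12 to 48 months.

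The median moves by 0 to about 2 months, and not at all when it falls before about 25 months.

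For scale, take a case with non-responder medians 4 and 14 months, responder medians 20 and 18, and 20% responders. The 90% sampling half-width at N = 57 is about ±12 points at 36 months and ±13 at 48, against biases of about +2 and +5.

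**Arm A, two readings of EOT.** Assumed: 20% to 50% of subjects with median remission 60 months, the rest 12; retreatment median 8 months; post-EOT survival median 18 months; death hazard 0.003 per month before EOT.

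- EOT follows the final study treatment after progression: +0.4 points at 36 months and about +2 at 48.
- EOT is 30 days after the last dose before observation, for subjects still in remission when the cap is reached: durable responders are capped first. The difference is -6.5 to -9.8 points at 36 months and -10 to -16 at 48. A case with half at median remission 40 months and half at 12, and 6 months' retreatment, gave about -13 and -17.

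**The case against.** The strongest case against is that nothing dated in the plan is affected. The only scheduled analysis precedes the cap, the plan names no OS landmark or later OS analysis, and its named Kaplan-Meier landmarks are PFS at 6 or 12 months. OS is secondary and descriptive, with no test or decision rule. The size rests on assumed rates and is smaller than the sampling error. Stops for toxicity or choice (Section 6.5) and treatment beyond progression (Section 6.7) loosen the link between EOT and failure.

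All of this stands and limits the weight of the point. It does not remove it: Section 13.3 plans follow-up for 2 years after EOT, so later survival data will exist, and Section 13.7.2 would put them on the same unrestricted curve.

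A reader might go further and infer that late OS is too favourable in both arms. The documents do not support that for Arm A. Progression there leads to retreatment, so it is not EOT. For a durable responder who never restarts, the last dose falls at or before the OS origin; on the literal calendar wording that subject is capped first, and the bias turns downward.

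**Conclusion.** The point holds in limited form. Follow-up tied to each subject's own EOT makes OS censoring after about 24 to 25 months depend on outcome, and plain Kaplan-Meier does not allow for it. The response endpoints, the primary analysis as scheduled and OS to 24 months stand.

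For Arm B the likely bias is upward, in the range shown above. The direction requires a higher death hazard in subjects two years off treatment than in those still treated. That is plausible because progression is the main reason to stop, but the documents do not establish it. For Arm A no direction can be stated until EOT is defined, so neither an upward claim nor a corrected median is warranted. Outside Arm A, the difference between Sections 6.6 and 8.1 is only about 30 days. Severity is minor.

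**What to change.** 1. Collect vital status on all subjects to one common calendar cut-off, using the phone and record review already planned. Censor OS only there, or at true loss to follow-up or withdrawal.
2. Use one follow-up anchor in Sections 6.6, 8.1 and 13.3 and the calendars. State which date counts as EOT, for survival follow-up, in Arm A subjects who stay in observation.
3. If contact is not extended, report the OS curve and median only to about 24 months from arm start. Alternatively, label later estimates as subject to dependent censoring and add a sensitivity analysis, for example one weighted for it.

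Items 1 and 2 cost a few extra phone or record checks and a protocol amendment. Item 3 costs only wording and any sensitivity analysis, but leaves no unqualified OS estimate beyond 24 months.
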